5.3. Screening/Baseline/Run-in Failures

Screen failures are defined as subjects who consent to participate in the clinical trial but are never subsequently randomized. In order to ensure transparent reporting of screen failure subjects, meet the Consolidated Standards of Reporting Trials publishing requirements, and respond to queries from Regulatory authorities, a minimal set of screen failure information is required including demography, screen failure details, eligibility criteria, and serious adverse events (SAEs; see Section 7.3.1.4).

5.4. Withdrawal/Stopping Criteria

The following actions must be taken in relation to a subject who fails to attend the clinical unit for a required study visit:

- The site must attempt to contact the subject and re-schedule the missed visit as soon as possible.
- The site must counsel the subject on the importance of maintaining the assigned visit schedule and ascertain whether or not the subject wishes to and/or should continue in the study.
- In cases where the subject is deemed ‘lost to follow up’, the investigator or designee must make every effort to regain contact with the subject (where possible, 3 telephone calls and if necessary a certified letter to the subject’s last known mailing address or local equivalent methods). These contact attempts should be documented in the subject’s medical record.
- Should the subject continue to be unreachable, only then will he/she be considered to have withdrawn from the study with a primary reason of “lost to follow up”.

A subject may withdraw from study treatment at any time at his/her own request, or may be withdrawn at any time at the discretion of the investigator for safety, behavioral, or administrative reasons. If a subject withdraws from the study, he/she may request destruction of any samples taken, and the investigator must document this in the site study records.

This protocol defines several clinical laboratory values, 12-lead ECG values, vital sign values, and additional safety criteria that, if observed and confirmed, mandate cessation of drug dosing and further evaluations. Any laboratory result that meets the stopping criteria should be repeated once to confirm the value before the subject is withdrawn from the study.

5.4.1. Liver Chemistry Stopping Criteria

Liver chemistry stopping and increased monitoring criteria have been designed to ensure subject safety and evaluate liver event etiology in alignment with the FDA guidance, “Drug-Induced Liver Injury: Premarketing Clinical Evaluation,” [DHHS, 2009].

Study treatment will be discontinued for a subject who meets the following criterion:

- ALT $\geq 3 \times$ ULN ([Appendix 2](#))

Refer to [Appendix 3](#), Liver Safety Required Actions and Follow-up Assessments, for details of the required assessments if a subject meets the above criterion.

5.4.1.1. Study Treatment Restart or Rechallenge

Study treatment restart or rechallenge after liver chemistry stopping criteria are met by any subject participating in this study is not allowed.

5.4.2. Hematological Stopping Criteria

Study treatment will be discontinued for a subject who meets any of the following criteria:

- Hemoglobin ≤ 9.9 g/dL (99 g/L)
- White blood cells $\leq 1999/\text{mm}^3$ ($1.910 \times 10^9/\text{L}$)
- Platelets $\leq 99.999 \times 10^9/\text{L}$

5.4.3. Renal Stopping Criteria

Study treatment will be discontinued for a subject who meets any of the following criteria:

- Persistent (confirmed on recheck) elevation of serum creatinine (>0.3 mg/dL) without an alternative cause identified
- Albumin to creatinine ratio ≥ 0.03 mg/mg
- New blood in urinalysis confirmed by microscopy without an alternative cause identified

5.4.4. QTc Stopping Criteria

The *same* QT correction formula *must* be used for *each individual subject* to determine eligibility for and discontinuation from the study. This formula may not be changed or substituted once the subject has been enrolled.

- For example, if a subject is eligible for the protocol based on corrected QT interval using Bazett’s formula (QTcB), then QTcB must be used for discontinuation of this individual subject as well.

Once the QT correction formula has been chosen for a subject's eligibility, the *same formula* must continue to be used for that subject *for all QTc data being collected for data analysis*. Safety ECGs and other non-protocol specified ECGs are an exception.

The QTc should be based on single or averaged QTc values of triplicate ECGs obtained over a brief (e.g., 5 to 10 minute) recording period.

Study treatment will be discontinued for a subject who meets either of the following criteria:

- QTc >500 msec OR uncorrected QT >600 msec
- Change from baseline QTc of >60 msec

Withdrawal of subjects will be based on an average QTc value of triplicate ECGs. If an ECG demonstrates a prolonged QT interval, then 2 more ECGs will be obtained over a brief period of time (e.g., 5 to 10 minute) and then the averaged QTc values of the 3 ECGs will be used to determine whether the subject should be discontinued from the study.

5.4.5. Vital Signs Stopping Criteria

Study treatment will be discontinued for a subject who meets any of the following criteria:

- Systolic blood pressure (BP) >160 mm Hg for >1 hour
- Diastolic BP >100 mm Hg for >1 hour
- Heart rate >120 beats per minute for >1 hour

Vital signs should be taken with the subject in a semi-supine position, having rested in this position for at least 5 minutes. Repeat measurements should be taken within 5 minutes with the subject in the same physical position.

5.4.6. Other Safety Dose Adjustment/Stopping Criteria

For an individual study participant, additional stopping criteria include, but are not limited to:

- Severe signs or symptoms, or significant changes in any of the safety assessments, that put the safety of the individual at risk (e.g., ECG, vital signs, laboratory tests, etc.), as judged by the investigator in consultation with the medical monitor if necessary

5.4.7. Additional Safety Stopping Criteria

Individual subjects, dosed with GSK3342830 who have experienced the following should be considered for potential discontinuation in consultation with the GSK medical monitor:

- Any Grade 4 AE
- Grade 3 gastrointestinal AE (see [Appendix 6](#))
 - *If a subject has 3 or more unformed stools in a 24-hour time frame, see [Appendix 10](#) to determine if samples should be collected for *Clostridium difficile* testing.*
- Grade 3 renal or urinalysis finding (see [Appendix 6](#))
- Severe hypersensitivity
- Anaphylaxis (see [Appendix 7](#))
- Subjects with a systolic BP of <90 mm Hg or a change in systolic BP from baseline of 30 mm Hg with symptoms. Vital signs should be taken with the subject in a semi-supine position, having rested in this position for at least 5 minutes and findings are confirmed upon repeat measurements taken within 5 minutes with the subject in the same physical position.

Data will be reviewed by the investigator and sponsor for consideration of potential study stopping if:

- Two (2) or more subjects, within a dose level, receiving GSK3342830 experience a Grade 3 renal or urinary AE that is deemed possibly or probably related to study drug by the investigator.
- Two (2) or more subjects, within a dose level, receiving GSK3342830 experience Grade 3 hypersensitivity related AE that is deemed possibly or probably related to study drug by the investigator.
- Two (2) or more subjects, within a dose level, receiving GSK3342830 experience a Grade 3 AE of rash that is deemed possibly or probably related to study drug by the investigator.
- Two (2) or more subjects, within a dose level, receiving GSK3342830 experience a Grade 3 vital sign (heart rate or BP) abnormality that is considered an AE and is deemed possibly or probably related to study drug by the investigator. Vital signs should be taken with the subject in a semi-supine position, having rested in this position for at least 5 minutes and findings are confirmed upon repeat measurements taken within 5 minutes with the subject in the same physical position.
- One (1) or more subjects receiving GSK3342830 experience anaphylaxis that is deemed possibly or probably related to study drug by the investigator.

The grading for AEs is based on the US National Institute of Allergy and Infectious Diseases Division of Microbiology and Infectious Diseases (DMID) Adult Toxicity Table (see [Appendix 6](#)).

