Hematologic findings	
Red Blood Cell (RBC) related changes
 
 • Decreases in RBC count, hemoglobin (Hgb), hematocrit (Hct; 2000 mg/kg/day in males and females) 
 • Peaked at Week 2 (-10% to -20% versus pre-dosing values) • Accompanied by increase in reticulocytes • RBC findings considered secondary to: 
 • Ongoing inflammation from infusion site reactions (above) • Contribution from high osmolality infusion • Hemolysis, iron depletion (catechol) or other direct mechanism of drug not considered present • Evidence of recovery by end of follow-up 
Other hematologic findings
 
 • Findings considered secondary to ongoing inflammation at the infusion site • Increases in neutrophils and concomitant decreases in lymphocyte % • Decreased fibrinogen • Prolongation of activated partial thromboplastin time • Decreases in albumin and albumin/globulin ratio • Increase in total protein (due to globulin increase) • development of iliac lymph node germinal center • Findings were reversible in follow-up 	
 • Reduced osmolality infusions • Normal white blood cell (WBC) count, Hgb, Hct, and platelets on study entry • Follow for signs or symptoms of anemia • Follow regular clinical labs (WBC, Hgb, Hct, reticulocyte count, and platelets) 
Stopping criteria
 
 • Hemoglobin ≤ 9.9 g/dL (99 g/L) • White blood cell $\leq 1999/\text{mm}^3$ ($1.910 \times 10^9/\text{L}$) • Platelets $\leq 99.999 \times 10^9/\text{L}$
Increased tidal volume in rat respiratory study	
 • Only at high dose (2000 mg/kg) • 22.9% at 30 minutes after completion of infusion • Changes considered to be minimal 
 • Magnitude within the range of physiological changes • No changes were seen in minute volume • Not statistically significant • May reflect high individual variability 	
 • Conduct study in inpatient Phase I clinical unit • Frequent vital sign capture during study • 6000 mg maximum dose maintains 2.1\times margin relative to the NOEL of 1000 mg/kg

Potential Risk of Clinical Significance	Summary of Data/Rationale for Risk	Mitigation Strategy

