Serotonin (5-HT)-3 in vitro binding assay	
 • “Moderately” positive with 39% effect at 100 mmol (78 µg/mL) • High dose Cmax will reach similar concentration • No clear in vivo correlation from toxicology studies 
 • Possible BP effect in monkey cardiovascular study • Poor central nervous system penetration (approximately 3% blood) 	
 • Precautions c/w those indicated to mitigate the BP effect seen in monkey cardiovascular study • Enroll healthy subjects not on medications to avoid additive arrhythmogenic potential
Other		
Neurologic findings (seizures)	
 • Known risk (seizures) for some β-lactams and cephalosporins • Seen pre-clinically with lead compound • No adverse findings to 2000 mg/kg/ day × 4 weeks in rats or monkeys • Central nervous system administration study in rats negative 	
 • Specifically assess for negative history of seizures in past medical history at screening • Close monitoring during infusion in an acute care setting
Rash/Dermatologic toxicity	
 • Rash is a common adverse event (AE) of β-lactam antibiotics. Range of manifestations and severity from mild morbilliform drug eruption to hives, Erythema multiforme (EM), Stevens-Johnson syndrome (SJS) and toxic epidermal necrolysis (TEN) in rare cases 	
 • Exclude individuals with history of rash to penicillins or cephalosporins • Exclude individuals with history of EM/SJS/TEN to any medication • Close monitoring • Discontinuation criteria 
 • Any rash of Grade 3 or greater severity • Any rash characterized by: 
 • Hives • Concomitant fever or other symptoms suggesting systemic manifestations • Blistering • Ocular or genital involvement • Access to standard interventions (antihistamines, steroids if indicated, intensive care unit/burn unit care in worst case)
Anaphylaxis/hypersensitivity	
 • Common to all β-lactam antibiotics 
 • Approximately 10% cross reaction between cephalosporins and penicillins • Guinea pig immunotoxicity model negative 	
 • Conduct study in inpatient Phase I clinical unit • “Crash” cart availability • Exclude subjects with history of penicillin allergy

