12.6. Appendix 6: DMID Adult Toxicity Tables for AE Assessment

ESTIMATING SEVERITY GRADE: For abnormalities NOT found elsewhere in the Toxicity Tables, use the following scale to estimate grade of severity:

GRADE 1	Mild	Transient or mild discomfort (<48 hours); no medical intervention/therapy required
GRADE 2	Moderate	Mild to moderate limitation in activity – some assistance may be needed; no or minimal medical intervention/therapy required
GRADE 3	Severe	Marked limitation in activity, some assistance usually required; medical intervention/therapy required, hospitalizations possible
GRADE 4	Life-threatening	Extreme limitation in activity, significant assistance required; significant medical intervention/therapy required, hospitalization or hospice care probable

SERIOUS OR LIFE-THREATENING AEs: ANY clinical event deemed by the investigator to be serious or life-threatening should be considered a Grade 4 event. Clinical events considered to be serious or life-threatening include, but are not limited to: seizures, coma, tetany, diabetic ketoacidosis, disseminated intravascular coagulation, diffuse petechiae, paralysis, acute psychosis, and severe depression.

COMMENTS REGARDING THE USE OF THESE TABLES

- Standardized and commonly used toxicity tables (Division of AIDS, National Cancer Institute’s Common Toxicity Criteria, and World Health Organization) have been adapted for use by the Division of Microbiology and Infectious Diseases (DMID) and modified to better meet the needs of participants in DMID trials.
- For parameters not included in the following Toxicity Tables, sites should refer to the “Guide for Estimating Severity Grade” located above.
- Criteria are generally grouped by body system.
- Some protocols may have additional protocol-specific grading criteria, which will supersede the use of these tables for specified criteria.

HEMATOLOGY				
	Grade 1	Grade 2	Grade 3	Grade 4
Hemoglobin	9.5 to 10.5 g/dL	8.0 to 9.4 g/dL	6.5 to 7.9 g/dL	<6.5 g/dL
Absolute Neutrophil Count	1000 to 1500 /mm ³	750 to 999 /mm ³	500 to 749 /mm ³	<500 /mm ³
Platelets	75,000 to 99,999 /mm ³	50,000 to 74,999 /mm ³	20,000 to 49,999 /mm ³	<20,000 /mm ³
White Blood Cells	11,000 to 13,000 /mm ³	13,000 to 15,000 /mm ³	15,000 to 30,000 /mm ³	>30,000 or <1000 /mm ³
% Polymorphonuclear Leukocytes + Band Cells	>80%	90 to 95%	>95%	N/A

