Mucocutaneous	Erythema; pruritus	Diffuse, maculo papular rash, dry desquamation	Vesiculation or moist desquamation or ulceration	Exfoliative dermatitis, mucous membrane involvement or erythema, multiforme or suspected Stevens-Johnson or necrosis requiring surgery
Induration	<15 mm	15 to 30 mm	>30 mm	N/A
Erythema	<15 mm	15 to 30 mm	>30 mm	N/A
Edema	<15 mm	15 to 30 mm	>30 mm	N/A
Rash at injection site	<15 mm	15 to 30 mm	>30 mm	N/A
Pruritus	Slight itching at injection site	Moderate itching at injection extremity	Itching over entire body	N/A
N/A = not applicable.				

SYSTEMIC				
	Grade 1	Grade 2	Grade 3	Grade 4
Allergic reaction	Pruritus without rash	Localized urticarial	Generalized urticarial; angioedema	Anaphylaxis
Headache	Mild, no treatment required	Transient, moderate; treatment required	Severe; responds to initial narcotic therapy	Intractable; requires repeated narcotic therapy
Fever: oral	37.7 to 38.5°C or 100.0 to 101.5°F	38.6 to 39.5°C or 101.6 to 102.9°F	39.6 to 40.5°C or 103 to 105°F	>40°C or >105°F
Fatigue	Normal activity reduced <48 hours	Normal activity decreased 25 to 50%; >48 hours	Normal activity decreased >50%; cannot work	Unable to care for self

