be treated symptomatically until the rash resolves. Antihistamines, topical corticosteroids, or antipruritic agents may be prescribed. The subject should remain on the study to be followed for safety and pharmacokinetics as outlined in Section 7.1.

Generalized urticaria or angioedema (Grade 3 allergic reaction):

Subjects will permanently discontinue the study drug and be withdrawn from the trial. Subjects will be treated as clinically appropriate. Subjects should be followed up until resolution of the AE and standard management should be undertaken.

Anaphylaxis (Grade 4 allergic reaction):

Anaphylaxis is an immediate and potentially life-threatening systemic reaction to an exogenous stimulus e.g., a drug.

Anaphylaxis typically involves 2 or more body systems (cutaneous, respiratory, cardiovascular, neurologic, or gastrointestinal) usually within 60 minutes of exposure but can be delayed up to several hours and can less commonly be biphasic or protracted despite treatment.

The term anaphylaxis typically has been reserved for allergic, Immunoglobulin E-mediated immediate hypersensitivity reactions. Anaphylactoid responses (also included here) are clinically indistinguishable reactions that occur by non-antigen/antibody-mediated mechanisms. Both reactions produce clinical sequelae due to the massive release of mediators from mast cells and basophils but hypotension and associated cardiac AEs are less common in anaphylactoid reactions. In contrast to anaphylactic reactions, anaphylactoid reactions can occur upon initial exposure to exogenous stimulus.

Subjects will permanently discontinue the study drug and be withdrawn from the trial. Subjects will be treated as clinically appropriate. Subjects should be followed up until resolution of the AE and standard management should be undertaken.

Revised ACTG Toxicity Grade	Definitions	Investigator Action
Grade 1	Pruritus without rash	May continue therapy
Grade 2	Localized urticaria	May continue therapy
Grade 3	Generalized urticaria Angioedema	Discontinue therapy
Grade 4	Anaphylaxis	Discontinue therapy

12.8. Appendix 8: Modified List of Highly Effective Methods for Avoiding Pregnancy in Females of Reproductive Potential and Collection of Pregnancy Information

12.8.1. Modified List of Highly Effective Methods for Avoiding Pregnancy in Females of Reproductive Potential

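### The white-cell stopping limit carries a wrong SI conversion, and Section 5.4.7 leaves to discretion allergic reactions that Appendix 7 makes mandatory stops

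*Protocol*

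**What the plan says.** **White cell count.** Protocol Section 5.4.2 discontinues study treatment at a white cell count of 1999/mm³ or below and gives the SI equivalent in parentheses as 1.910 × 10⁹/L. The hematologic row of the Section 4.6.1 risk table prints the same pair. Section 5.4 adds that a laboratory result meeting a stopping criterion "should be repeated once to confirm the value before the subject is withdrawn from the study".

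**Severe allergic reactions.** Section 5.4.7 says that subjects dosed with GSK3342830 who have a listed event "should be considered for potential discontinuation in consultation with the GSK medical monitor". The list includes any Grade 4 AE, severe hypersensitivity, and anaphylaxis. Of these three, only anaphylaxis refers to Appendix 7. In the Appendix 6 allergic reaction row, Grade 3 is "Generalized urticarial; angioedema" and Grade 4 is anaphylaxis. For each of these two grades Appendix 7 states: "Subjects will permanently discontinue the study drug and be withdrawn from the trial". Its action table repeats the instruction. The opening text of Section 5.4 describes the protocol's laboratory, ECG, vital-sign and additional safety criteria as ones that, once observed and confirmed, require dosing to cease.

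**Hives.** The rash row of Section 4.6.1 has a list of discontinuation criteria. One entry reads "Any rash characterized by", and the first feature under it is hives, with no limit on grade or extent. Appendix 7 lets a subject with localized urticaria (Grade 2) continue at the investigator's discretion, provided there is no temperature above 38.5 °C, eosinophilia, respiratory involvement or internal organ involvement.

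**The concern.** A stopping rule should give one answer for one set of facts. Here a single mandatory laboratory limit has two values, and the SI value is the less protective. A mandatory clinical stop in an appendix becomes a matter for consultation in the section that carries the stopping criteria. Sections 5.4.1 to 5.4.5 all say that treatment will be discontinued, so the softer lead-in of Section 5.4.7 can be read as a deliberate lower category.

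These rules decide whether a healthy volunteer receives the next infusion. That matters mainly in Part 2, where infusions are about 8 hours apart. In Parts 1 and 3 each subject has one infusion, so an allergic-reaction stop could at most interrupt it, and the post-dose white-cell draws (Day 2 and follow-up) come after it.

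**Working it through.** **1. White cell conversion.**

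Input: 1999 cells/mm³ (Sections 4.6.1 and 5.4.2). Since 1 mm³ = 10⁻⁶ L, cells/L = cells/mm³ × 10⁶.

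- 1999 × 10⁶ = 1.999 × 10⁹/L. The printed 1.910 × 10⁹/L is not reproduced. Rounding 1.999 gives 2.0 or 1.999, never 1.910.
- Converted back, 1.910 × 10⁹/L is 1910/mm³. The gap is 1999 − 1910 = 89 cells/mm³, and 89/1999 = 4.5%.
- Check on the same list: hemoglobin 9.9 g/dL × 10 = 99 g/L, as printed. Platelets are given only as 99.999 × 10⁹/L, so there is no pair to check.

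The counts affected are those with 1.910 < v ≤ 1.999 (× 10⁹/L). The documents do not state the reporting precision, so the range is:

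| Decimals reported | Values stopping under mm³ but not under SI |
|---|---|
| 1 | none (1.9 stops under both, 2.0 under neither) |
| 2 | 8 (1.92 to 1.99) |
| 3 | 89 (1.911 to 1.999) |

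**2. Severe allergic reactions.** No arithmetic applies. The texts side by side:

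| Event | Section 5.4.7 | Appendix 7 |
|---|---|---|
| Generalized urticaria or angioedema (Grade 3) | Discretionary if treated as severe hypersensitivity; no reference to Appendix 7 | Permanent stop and withdrawal |
| Anaphylaxis (Grade 4) | Discretionary, with reference to Appendix 7; covered again by the bullet for any Grade 4 AE | Permanent stop and withdrawal |

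The opening of Section 5.4 agrees with Appendix 7. Section 5.4.7 is therefore the odd one out, and its reference to Appendix 7 leads to text that contradicts its own lead-in.

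**3. Hives.** Reading hives and urticaria as the same sign, the two texts differ only for localized urticaria with none of the four listed signs. Section 4.6.1 lists it as a reason to discontinue; Appendix 7 permits continuation.

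**4. Who could be affected.** Planned active subjects (Section 4.3):

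- Part 1: 6 cohorts × 6 = 36
- Part 2: 3 × 8 = 24
- Part 3: 8
- Total: 36 + 24 + 8 = 68

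Repeat dosing applies to 24/68 = 35%. The other 36 + 8 = 44 receive one infusion.

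**The case against.** The strongest reply is that practice would be right anyway. Appendix 7 is the specific text, it is mandatory in both its paragraph and its table, and the anaphylaxis bullet points to it. An investigator who stops dosing satisfies every section. Section 5.4.6 leaves room for judgement, and one related anaphylaxis already sends the study to review for possible stopping. Severe hypersensitivity is not defined in Section 5.4.7, so that part of the conflict is conditional. All of this stands and lowers the risk. It does not make the texts agree, and the reference does not reach the other two bullets.

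On the white cell count, subjects enter with normal counts, scheduled Part 2 hematology during dosing falls on Days 2, 5, 10 and 15 only, and a stopping value is repeated. A confirmed count inside an 89-cell band is remote. That also stands, but the figure is still a decision threshold and it is wrong.

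Four stronger readings are tempting and are not supported.

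- **That SAP results change with the unit applied.** SAP Section 10.7.1 converts to SI units for toxicity grading, not for stopping rules. The only low white-cell grade in the protocol's Appendix 6 is in the Grade 4 cell, ">30,000 or <1000" per mm³, and the SAP uses the same limit. No grade falls in the disputed band.
- **That the SAP counts every subject who met a stopping criterion.** The row in SAP Table 1.2 is one of the primary reasons for study withdrawal, so it covers withdrawn subjects by recorded reason. The row in Table 1.4 is a deviation category from the eCRF. Neither is derived from laboratory values.
- **That the Part 2 infusions still due after an event measure the effect.** That assumes dosing would go on after anaphylaxis, which Appendix 7 forbids, and there is no event rate to attach to it.
- **That localized urticaria must stop dosing.** The closing paragraph of Section 2.2 can be read as placing monitoring and management in Section 4.6 and stopping criteria in Section 5.4. On that reading the risk table is a summary and could equally be the text to amend.

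**Conclusion.** Two rules are wrong as written and should be fixed. The white-cell SI figure is a plain error, printed identically in two sections and less protective by 89 cells/mm³ (4.5%). Its practical effect is small, and nil if counts are reported to one decimal. Section 5.4.7 contradicts Appendix 7 and the opening of Section 5.4 for anaphylaxis, and for severe hypersensitivity where that means generalized urticaria or angioedema. This is the more consequential of the two because it concerns a foreseeable risk: Section 4.6.1 describes anaphylaxis and hypersensitivity as common to all β-lactams.

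The hives mismatch is minor and narrow, and which rule is right is a clinical choice.

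The effect on dosing is essentially confined to about 24 Part 2 subjects. No frequency of events is assumed. Nothing here touches an endpoint, an estimate or the sample size, and a reader should not infer that anyone would be re-dosed after anaphylaxis under this protocol.

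**What to change.** 1. In Sections 4.6.1 and 5.4.2, change 1.910 to 1.999 × 10⁹/L.
2. In Section 5.4.7, state that study treatment will be discontinued for Grade 3 or Grade 4 allergic reactions as set out in Appendix 7, and except these reactions from the discretionary bullet for any Grade 4 AE.
3. Have the sponsor's clinical team choose one rule for uncomplicated localized urticaria, then align the rash row of Section 4.6.1 with the Grade 2 text and action table of Appendix 7. No default is proposed here.

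The cost is protocol wording in one amendment. Design, sample size and assessments do not change.
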